Additional Objectives	In all randomized subjects the following analyses will be performed: 
 
• All-cause mortality and sudden cardiac death in various subgroups including sex, race, age continuous and dichotomized at 75 years, duration of diabetes, presence vs. absence of insulin therapy, HbA1c dichotomized at 8%, LVEF continuous and dichotomized at 40%, and other relevant subgroups
 
• Healthcare utilization assessed through adverse event reporting
 

Additional Pre-Specified Analyses	In subjects randomized to S-ICD the following analyses will be performed: 
 
• Frequency and outcomes of S-ICD Inappropriate Shocks
 
• Frequency and outcomes of S-ICD treated ventricular tachycardia (VT) and ventricular fibrillation (VF)
 
• Frequency and outcomes of S-ICD device complications, including but not limited to: infection, device malfunction and electrode movement
 

Method of Assigning Patients to Treatment	Subjects will be randomized 2:1 (S-ICD:CMT). Randomization will occur electronically using the clinical data collection system.
Follow-up Schedule	
 
• Screening and Consent
 
• Baseline data collection
 
• Implant procedure (device subjects only)
 
• 1 month visit (in-clinic visit for S-ICD subjects and phone contact for CMT subjects)
 
• 6 month phone contact (conduct annually thereafter at months 18, 30, 42, etc.)
 
• 12 month visit (conduct annually thereafter at months 24, 36, 48, etc.) 
 
○ S-ICD Arm 12 Month in-clinic follow-up
 
○ CMT Arm 12 Month phone follow-up
 
 
 

Study Duration	The study is expected to enroll over a 48 month period with an average of 2.6 years of follow-up. Note: the length of the study is based on the accumulation of endpoint events and the hazard ratio.
Eligibility Criteria	Note: The most recent evaluations, measurements or test results in the medical record must be used to assess inclusion and exclusion criteria.

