	
 
• Unstable angina with need for outpatient treatment or hospitalization (change/addition of anti-anginal medication and/or coronary revascularization), within 3 calendar months prior to the consent date
 
• Angiographic evidence of coronary disease in a patient that is a candidate for coronary revascularization and is likely to undergo CABG or PCI in the next 3 calendar months
 
• High risk for arterial embolism (e.g. presence of mobile left ventricular thrombus)
 
• Hemodynamically significant congenital heart disease, aortic valvular heart disease, or amyloid heart disease
 
• Baseline body mass index <math>> 45 \text{ kg/m}^2</math>
 
• On a heart transplant list or likely to undergo heart transplant within one calendar year
 
• Presence of any other disease, other than the subject's cardiac disease, that in the opinion of the investigator is likely to significantly reduce the patient's likelihood of survival for the duration of the trial (e.g. cancer, liver failure).
 
• Unwillingness or inability to cooperate with the protocol
 
• Resides at such a distance from the enrolling site so travel to follow-up visits would be unusually difficult
 
• Reversible causes of heart disease (e.g. viral myocarditis or tachycardia induced cardiomyopathy)
 
• Participation in other clinical trials (observational registries are allowed with approval from the CDC)
 
• Does not anticipate residing in the vicinity of the enrolling site for the duration of the trial
 
• Unwillingness to sign the consent for participation
 

Statistical Methods	
Primary Statistical Hypothesis	Post-MI diabetes patients with a relatively preserved left ventricular ejection fraction will have reduced mortality from S-ICD as compared to CMT.
Statistical Test Method	Wang-Tsiatis group sequential design based on monitoring the log-rank statistic for time-to-death, with stochastic curtailment based on conditional power and sample size re-estimation based on overall recruitment, withdrawal, and event rates.
Sample Size Parameters	1800 patients are expected to yield a maximum of 454 deaths, which provides 80% power at a two-sided significance level of 5% to detect a HR of 0.75.

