#### 12.1.1.2. Sample Size

[figure not shown]
1800 men and women from the U.S., Europe, and Israel will be enrolled based on the following assumptions:

- **Wang-Tsiatis ( $\Delta=0.1$ ) Design with K=18 Possible Analyses**
- **2:1 randomization (S-ICD:CMT)**
- **$\alpha = 5\%$  (two-sided)**
- **Power = 80%**
- **Hazard ratio of 0.75**
- **Attrition rate of 10%**

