**Figure 12-1: Stopping and Decision Boundaries for the Design**

**AAA:** S-ICD more effective    **BBB:** Med Rx more effective    **CCC:** no difference

Reaching the upper boundary (A) leads to a decision in favor of the S-ICD, reaching the lower boundary (B) in favor of the medical treatment, and reaching the central part (C) of the vertical boundary results in a ‘no difference’ conclusion. Hence, a no-difference conclusion is only possible at the final analysis.

Numerical values of the boundaries, derived using SAS version 9.4, are in **Table 12.1-1**, along with the schedule of cumulative  $\alpha$ -spending and cumulative power for hazard ratios (HR’s) of 0.70 and 0.75. The cumulative power reaches 80% at analysis 18 for a HR of 0.75. For a HR of 0.70, the cumulative power exceeds 80% by analysis 14 and reaches 94% at the final analysis. Although this design could require as many as 454 events to

get to the final (18th) analysis, the trial would be expected to terminate at the 13th analysis if the HR is 0.75 and at the 10th analysis if the HR is 0.70.

**Table 12.1-1: Coordinates of the Upper and Lower Stopping Boundaries and the Associated  $\alpha$ -Spending and Cumulative Power**

Analysis (Info %)	Variance	Events	Standardized Boundaries ( $\pm$ )	Nominal $\alpha$	$\alpha$ -Spending	Cumulative Power HR=0.75 HR=0.70	
1 (15)	15.1	68.0	4.62	0.00000	0.00000	0.0002	0.0006
2 (20)	20.1	90.6	4.12	0.00004	0.00004	0.0024	0.0060
3 (25)	25.2	113.3	3.77	0.00017	0.00018	0.0106	0.0250
4 (30)	30.2	136.0	3.50	0.00046	0.00054	0.0292	0.0649
5 (35)	35.3	158.6	3.29	0.00100	0.00122	0.0611	0.1273
6 (40)	40.3	181.3	3.12	0.00181	0.00230	0.1062	0.2081
7 (45)	45.3	204.0	2.98	0.00292	0.00386	0.1626	0.3001
8 (50)	50.4	226.6	2.85	0.00433	0.00590	0.2272	0.3960
9 (55)	55.4	249.3	2.75	0.00602	0.00846	0.2966	0.4893
10 (60)	60.4	271.9	2.65	0.00799	0.01150	0.3677	0.5759
11 (65)	65.5	294.6	2.57	0.01020	0.01502	0.4377	0.6532
12 (70)	70.5	317.3	2.49	0.01263	0.01898	0.5047	0.7201
13 (75)	75.5	339.9	2.43	0.01526	0.02334	0.5675	0.7766
14 (80)	80.6	362.6	2.36	0.01806	0.02806	0.6250	0.8235
15 (85)	85.6	385.3	2.31	0.02102	0.03314	0.6770	0.8617
16 (90)	90.6	407.9	2.26	0.02410	0.03850	0.7234	0.8924
17 (95)	95.7	430.6	2.21	0.02729	0.04414	0.7643	0.9169
18 (100)	100.7	453.2	2.16	0.03058	0.05000	0.8000	0.9361

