The standardized (Normal) log-rank statistic will be plotted against information at each analysis until a boundary is reached. The vertical boundary is at analysis 18, extending from  $-2.16$  to  $+2.16$ . Alternative boundary scales are presented in **Table 12.1-2**. The Score statistic boundaries are based on the cumulative (non-standardized) log-rank statistic (and thus are simply the standardized boundaries multiplied by the square root of variance in Table 12.1-1). The boundaries based on the Maximum Likelihood Estimator (MLE) of the HR show how extreme the treatment effect would have to be in order to reach a stopping boundary early in the trial. In particular, the HR would have to be smaller than 0.31 or larger than 3.28 to stop on the first analysis. These bounds narrow considerably as the interim analyses progress, but they still represent clinically

meaningful effects at the final (18th) analysis. Specifically, the HR would have to be smaller than 0.81 or larger than 1.24 in order to be significant ( $p < 0.05$ ) at the final analysis; any HR estimate between 0.81 and 1.24 at the final analysis would result in reaching boundary C (the no-difference conclusion).

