The trial will likely end earlier if the S-ICD is effective (even though events will accumulate more slowly). In particular, if the true HR is 0.75 and assumptions (1)-(4) hold, the trial will require 56-71 months. A HR of 0.70 would require 4-6 fewer months. The worst case scenario is a HR of 1.00 and a 20% event rate, which could require 83 months (See **Table 12.1-4**).

Adaptive trial design elements will be used to guard against the possibility of a negative or overly lengthy trial. Stochastic curtailment based on conditional power (i.e. the chance of reaching boundary A or B under the alternative hypothesis, given the currently available data) will be used as a basis for terminating the study early due to futility. If the chance of reaching boundary C becomes so large that the no-difference conclusion is practically inevitable, then it would be futile to continue the study.

Simulations were used to determine an appropriate threshold for conditional power in declaring futility. This involved repeatedly (1 million times for each scenario) generating the sequence of 18 log-rank test statistics (according to a multivariate normal distribution that depends on the set of information levels in Table 12.1-1 and the true HR^25), calculating the conditional power (a function of observed log-rank test statistics, the information levels in Table 12.1-1, the overall significance level, and the true HR^25) under the alternative hypothesis (HR = 0.75) after interim analyses 1-17, and determining the outcome (reaching boundary A, B, or C, or declaring futility early). Simulations were conducted under a variety of true HR's in order to find a suitable conditional power threshold. Choosing a value of 0.0001% appears appropriate because (1) there is virtually no effect on the significance level or power; (2) declaring futility is practically impossible until the 15th analysis; (3) there is a good chance (64%) of declaring futility early if the true HR is 1.0; and (4) there is little chance (2%) of declaring futility early if

April 2016

the true HR is 0.75. Complete results of the simulation study using a conditional power threshold of 0.0001% are shown in **Table 12.1-3**. Note that the simulation size implies a standard error for percentages of at most 0.05%, and thus percentages can be assumed accurate to  $\pm 0.2\%$  (with 99.99% confidence).

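### A final analysis that crosses no boundary is pre-specified as 'no difference', although it is only non-rejection in a superiority test and can leave the design hazard ratio of 0.75 open

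*Combined protocol and SAP*

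**What the plan says.** The primary endpoint, all-cause mortality, is tested for superiority in a group sequential design. The synopsis gives a "maximum of 454 deaths, which provides 80% power at a two-sided significance level of 5% to detect a HR of 0.75".

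Section 12.1.1.3 and Figure 12-1 define three decisions. Boundary A favours the S-ICD, boundary B favours medical therapy, and "reaching the central part (C) of the vertical boundary results in a ‘no difference’ conclusion". The text adds that "a no-difference conclusion is only possible at the final analysis". After Table 12.1-1 the rule is put on the hazard ratio scale: "any HR estimate between 0.81 and 1.24 at the final analysis would result in reaching boundary C (the no-difference conclusion". The column heading for C in Table 12.1-3 repeats the label.

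Section 12.1.1.3 also lists futility as a separate way for the trial to end. Section 12.1.1.3.2 explains when that applies: "If the chance of reaching boundary C becomes so large that the no-difference conclusion is practically inevitable". Section 14.2 describes the DSMB's futility review in similar terms.

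Section 12.3 plans a Cox hazard ratio and 95% confidence limits, both adjusted for the sequential design. It does not link them to the conclusion drawn when C is reached.

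**The concern.** Failing to cross A or B means only that superiority was not shown in either direction. An affirmative finding of no difference would need a margin, and an interval lying inside it; the plan defines no margin. Read literally, the decision rule could therefore declare the two arms no different on mortality when the data cannot exclude the 25% reduction the trial was sized to detect. By symmetry, the same holds for a harm of equal size.

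A second, smaller matter is timing. The conclusion is tied to Analysis 18, yet the trial may stop earlier for futility because that same conclusion is expected. The plan does not say what is concluded at such a stop.

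**Working it through.** **Inputs**
- Two-sided 5% level, 80% power, HR 0.75, at most 454 deaths (synopsis).
- Wang-Tsiatis boundaries with shape parameter 0.1, "Design with K=18 Possible Analyses" (section 12.1.1.2).
- Allocation: "Subjects will be randomized 2:1 (S-ICD:CMT"). Information per event is therefore 2/3 × 1/3 = 2/9.
- Analysis 18 in Table 12.1-1: variance 100.7, 453.2 events, critical value 2.16, nominal alpha 0.03058.
- Analysis 18 in Table 12.1-2: HR bounds 0.806 and 1.240.
- Table 12.1-3, row for true HR 0.75: 80.0% A or B, 18.0% C, 2.1% early futility.

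**Step 1. Reproduce the plan's figures**
- Information: 453.2 × 2/9 = 100.7, as tabulated.
- Solving the Wang-Tsiatis boundaries numerically for two-sided alpha 0.05 and 80% power gives a final critical value of 2.162, maximum information 100.73 and 453.3 events. All 18 boundaries and the cumulative powers agree with Table 12.1-1.
- Final HR bound: exp(−2.162/√100.73) = 0.806, and its reciprocal is 1.240. Both agree with Table 12.1-2.
- The plan states: "The cumulative power reaches 80% at analysis 18 for a HR of 0.75". The recalculation gives 80.0%, with crossing of B contributing less than 0.001%, so non-crossing is 20.0%. Table 12.1-3 gives 18.0 + 2.1 = 20.1%, which agrees within rounding.

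Simulating one million trials with a futility rule at conditional power 0.0001% gave C 16.7% and futility 3.3% at HR 0.75. This split differs somewhat from the table, probably because conditional power was computed differently. The sum, 20.0%, agrees.

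**Step 2. What an estimate inside C can exclude**
- SE(log HR) = 1/√100.7 = 0.0997.
- With critical value 2.16, the limits are the estimate divided and multiplied by exp(2.16 × 0.0997) = 1.240.
- Estimate 0.81: 0.81/1.240 = 0.65, to just above 1.00.
- Estimate 0.85: 0.85/1.240 = 0.69, to 0.85 × 1.240 = 1.05.
- The lower limit exceeds 0.75 only if the estimate exceeds 0.75 × 1.240 = 0.93.
- Share of C at or below that value, on the log scale: ln(0.93/0.806) / ln(1.240/0.806) = 0.143/0.431 = 33%.
- With an unadjusted 1.96, the cut-off is 0.75 × exp(1.96 × 0.0997) = 0.91 and the share is about 29%.
- On the harm side, an HR of 1/0.75 = 1.33 is not excluded for estimates from 1.33/1.240 = 1.075 up to 1.24. Only about the middle third of C excludes both a design-size benefit and a design-size harm.

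**Step 3. What a futility stop can exclude**

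In the recalculation, conditional power under HR 0.75 falls below 0.0001% only in these ranges. The lower limits use each look's own critical value.
- Analysis 15: estimates above about 1.01. Lower limit 1.013 × exp(−2.31/√85.6) = 0.79, which excludes 0.75.
- Analysis 16: estimates above about 0.96. Lower limit 0.960 × exp(−2.26/√90.6) = 0.757, which excludes 0.75.
- Analysis 17: estimates above about 0.905. Lower limit 0.905 × exp(−2.21/√95.7) = 0.72, so stops with estimates of about 0.905 to 0.94 do not exclude 0.75.

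At true HR 0.75, Table 12.1-3 places 1.6 of the 2.1 percentage points of futility at Analysis 17. At true HR 1.00 it gives a 64.2% chance of an early futility stop, so with no true effect the most likely ending is one without a stated conclusion.

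**The case against.** The strongest reply is that this is only a label. Section 12.1.1.3 puts 'no difference' in quotation marks, and the sentence placing HR 0.81 to 1.24 in C also says that values outside that range are the significant ones. C is therefore visibly the non-significant region, and no equivalence is claimed. Section 12.3 already plans the adjusted HR and limits, so a reader would see the interval. This limits the harm, and nothing in the documents says that the published report would use the label alone. It does not remove the fault: C is the pre-specified conclusion for the primary endpoint, and section 12.3 neither overrides nor qualifies it.

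Four stronger readings are tempting, and the documents do not support them.
- A reader might infer that 20% of trials with a real 25% reduction suffer an added error. That 20% is the planned type II error of an 80%-power design, openly tabulated.
- A reader might infer that all 20.1% would be labelled 'no difference'. Table 12.1-3 lists futility separately, so strictly only the 18.0% ending in C carries the label. Futility stops at Analyses 15 and 16 already exclude 0.75.
- A reader might infer that a significant result is being suppressed at an estimate of 0.81. Its z of 2.11 gives a nominal p of about 0.034, above the final 0.03058, and its interval includes 1. It is correctly non-significant.
- A reader might infer that the timing sentence flatly contradicts the futility rule. Boundary C does exist only at Analysis 18, and futility is listed as another route to ending. What remains is a gap: the earlier stop is justified by a conclusion it is not itself given.

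**Conclusion.** The concern holds as a fault in the conclusion attached to boundary C. Followed as written, the rule concludes 'no difference' for every final HR estimate from about 0.81 to 1.24. For estimates up to about 0.93, one third of that range on the log scale, the limits still include the effect the trial was designed to find. At a true HR of 0.75 the plan's own table sends 18.0% of trials to C. The error rates, boundaries, event count and sample size stand as calculated.

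The 0.93 cut-off assumes final information of 100.7 and uses the critical value 2.16 as a stand-in for the adjusted limits of section 12.3, which rest on maximum-likelihood ordering and could fall somewhat differently; an unadjusted interval gives 0.91. The futility ranges come from a recalculation that stops more often than Table 12.1-3 reports (73.9% against 64.2% at HR 1.00), so they are approximate. The conclusion also assumes that no other document, such as the DSMB charter, redefines C.

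**What to change.** - In section 12.1.1.3, Figure 12-1 and the heading of Table 12.1-3, relabel C as 'neither benefit nor harm shown'.
- State that the result is then interpreted from the sequentially adjusted HR and 95% limits of section 12.3, and that a 25% reduction is ruled out only if the lower adjusted limit exceeds 0.75.
- Reconcile the sentence confining the conclusion to the final analysis with the futility rule in sections 12.1.1.3, 12.1.1.3.2 and 14.2. Giving a futility stop the same 'neither benefit nor harm shown' conclusion, read with the same adjusted interval, closes the gap.

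The cost is wording in the protocol and SAP, and in the DSMB charter if it repeats the label. No boundary, event number, sample size or error rate changes: non-crossing at true HR 0.75 stays at 20.0%. The downside is a less definite statement after a non-significant result.

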**Table 12.1-2 Alternative Scales for the Upper and Lower Stopping Boundaries: Score Statistic and MLE of HR**

Analysis (Info %)	Variance	Events	Score Statistic Boundaries ( $\pm$ )	HR MLE Boundaries	
				Upper (Stop on A if HR <)	Lower (Stop on B if HR >)
1 (15)	15.1	68.0	17.95	0.305	3.281
2 (20)	20.1	90.6	18.48	0.400	2.502
3 (25)	25.2	113.3	18.89	0.472	2.118
4 (30)	30.2	136.0	19.24	0.529	1.890
5 (35)	35.3	158.6	19.54	0.574	1.741
6 (40)	40.3	181.3	19.80	0.612	1.635
7 (45)	45.3	204.0	20.04	0.643	1.556
8 (50)	50.4	226.6	20.25	0.669	1.495
9 (55)	55.4	249.3	20.44	0.691	1.446
10 (60)	60.4	271.9	20.62	0.711	1.407
11 (65)	65.5	294.6	20.79	0.728	1.374
12 (70)	70.5	317.3	20.94	0.743	1.346
13 (75)	75.5	339.9	21.09	0.756	1.322
14 (80)	80.6	362.6	21.22	0.768	1.301
15 (85)	85.6	385.3	21.35	0.779	1.283
16 (90)	90.6	407.9	21.47	0.789	1.267
17 (95)	95.7	430.6	21.59	0.798	1.253
18 (100)	100.7	453.2	21.70	0.806	1.240

Any sample size that can eventually yield 454 events could be chosen, and the two-sided significance level of 5% and power of 80% at a HR of 0.75 would be maintained.

Making assumptions and choices about the recruitment period, the event rate in CMT-only patients, drop-out rates, the randomization ratio, and the desired maximum duration of the trial, an appropriate sample size can be determined.

### 12.1.1.3.1 Computations for Total Sample Size of 1,800 subjects

Computations show that a total sample size of  $n = 1,800$  will meet requirements (1)-(5) below (see section 28.3 for details):

- (1) Recruitment rates of 25 patients per month (ppm) in year 1, 35 ppm in year 2, and 45 ppm in years 3-4 (1800 total patients over 48 months).
- (2) A 3-year cumulative event rate of 20%, 25%, or 30% in CMT-only patients.
- (3) A 5-year cumulative drop-out rate of 10% in each arm.
- (4) A randomization ratio of 2:1, S-ICD to CMT only.
- (5) The trial should end within 6 years (2 years after recruitment ends).

### 12.1.1.3.2 Computations for Sample Size Expected to Generate 454 Events

Computation of a sample size that would be expected to generate 454 events depends on:

- (1) The number of patients recruited each month:  $P_1$  in month 1,  $P_2$  in month 2, ...
- (2) The overall event rate. If the 3-year cumulative event rate is 25% in CMT-only patients, and the HR is 0.75, then the overall rate is a weighted average (due to 2:1 randomization) of 0.25 (weight = 1) and  $1 - (1 - 0.25)^{0.75} = 0.194$  (weight=2). That works out to 21.3% over 3 years, or a monthly event rate (MER) of 0.59%.
- (3) The 5-year cumulative drop-out rate of 10% in each arm. That is a monthly drop-out rate (MER) of 0.17%.

In the first month,  $P_1$  patients are enrolled, and assuming uniformly distributed enrollment times, they are expected to contribute  $P_1/2$  months of follow-up. The expected numbers of events and withdrawals at the end of the first month are then  $(P_1/2)*MER$  and  $(P_1/2)*MDR$ , respectively. The expected number of patients remaining at risk entering month 2 is then  $P_1*(1 - MER/2 - MDR/2)$ . These monthly computations can be done sequentially, where at month  $j$ :

- $R_{j-1}$  patients are still at-risk from month  $j-1$
- $P_j$  patients are enrolled uniformly in month  $j$
- Expected follow-up time in month  $j$ :  $R_{j-1} + P_j/2$
- Expected numbers of events in month  $j$ :  $(R_{j-1} + P_j/2)*MER$
- Expected withdrawals in month  $j$ :  $(R_{j-1} + P_j/2)*MDR$
- Expected number of patients remaining at risk entering month  $j+1$ :  $R_{j-1}*(1 - MER - MDR) + P_j*(1 - MER/2 - MDR/2)$ .

Setting  $P_j = 25$  for  $j = 1, \dots, 12$ ,  $P_j = 35$  for  $j = 13, \dots, 24$ ,  $P_j = 45$  for  $j = 25, \dots, 48$ , and  $P_j = 0$  for  $j > 48$ , the expected counts that appear in Table 27.3-1 are obtained.

Table 27.3-1 in the Appendix provides a monthly accounting of patients with projections of events (assuming a HR of 0.75 and a 25% rate in (2)), withdrawals, and timing of analyses for this design. The 1st analysis should be performed at 15% information (69 events) and is projected to occur at month 30 with 990 patients enrolled. Further analyses would be performed at 5% increments of information (every 23 events), and these are expected to occur approximately every 3-4 months.

The trial will likely end earlier if the S-ICD is effective (even though events will accumulate more slowly). In particular, if the true HR is 0.75 and assumptions (1)-(4) hold, the trial will require 56-71 months. A HR of 0.70 would require 4-6 fewer months. The worst case scenario is a HR of 1.00 and a 20% event rate, which could require 83 months (See **Table 12.1-4**).

Adaptive trial design elements will be used to guard against the possibility of a negative or overly lengthy trial. Stochastic curtailment based on conditional power (i.e. the chance of reaching boundary A or B under the alternative hypothesis, given the currently available data) will be used as a basis for terminating the study early due to futility. If the chance of reaching boundary C becomes so large that the no-difference conclusion is practically inevitable, then it would be futile to continue the study.

Simulations were used to determine an appropriate threshold for conditional power in declaring futility. This involved repeatedly (1 million times for each scenario) generating the sequence of 18 log-rank test statistics (according to a multivariate normal distribution that depends on the set of information levels in Table 12.1-1 and the true HR^25), calculating the conditional power (a function of observed log-rank test statistics, the information levels in Table 12.1-1, the overall significance level, and the true HR^25) under the alternative hypothesis (HR = 0.75) after interim analyses 1-17, and determining the outcome (reaching boundary A, B, or C, or declaring futility early). Simulations were conducted under a variety of true HR's in order to find a suitable conditional power threshold. Choosing a value of 0.0001% appears appropriate because (1) there is virtually no effect on the significance level or power; (2) declaring futility is practically impossible until the 15th analysis; (3) there is a good chance (64%) of declaring futility early if the true HR is 1.0; and (4) there is little chance (2%) of declaring futility early if

April 2016

the true HR is 0.75. Complete results of the simulation study using a conditional power threshold of 0.0001% are shown in **Table 12.1-3**. Note that the simulation size implies a standard error for percentages of at most 0.05%, and thus percentages can be assumed accurate to  $\pm 0.2\%$  (with 99.99% confidence).

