**Table 12.1-3 Simulation Results Using a Conditional Power Threshold of 0.0001%**

True HR	Chance (%) of Hitting Boundary A or B	Chance (%) of Hitting Boundary C (No Difference)	Chance (%) of Declaring Futility Before Analysis 18	Chance (%) of Declaring Futility at		
				Analysis 15	Analysis 16	Analysis 17
1.54	98.8	1.1	0.09	0.02	0.03	0.04
1.43	93.6	5.5	0.8	0.2	0.3	0.4
1.33	80.0	15.7	4.3	0.9	1.7	1.7
1.25	58.2	28.1	13.7	2.8	5.7	5.1
1.11	17.4	33.8	48.8	8.8	21.9	18.1
1.00	5.0	30.9	64.2	9.0	27.3	27.9
0.90	17.4	44.4	38.2	3.5	13.5	21.2
0.80	58.2	34.0	7.9	0.4	2.0	5.4
0.75	80.0	18.0	2.1	0.07	0.4	1.6
0.70	93.6	6.1	0.3	0.009	0.06	0.3
0.65	98.8	1.2	0.03	0.0003	0.004	0.02

The timing of these futility analyses will coincide with the scheduled interim analyses for efficacy, starting with Analysis 14 (projected at month 67; see Computations for Sample Size Expected to Generate 454 Events). This was selected because in none of the one million simulations was futility declared before Analysis 15.

Another adaptive design feature that will be used is sample size re-estimation.

Deviations from our assumed enrollment, withdrawal, and event rates could result in an overly lengthy trial (in calendar time). Current projections are to observe 454 events in 79 months. These projections will be updated as the trial nears full enrollment (1800 patients), and enrollment may be extended if needed to complete the trial on-time.

Because this is an event-driven trial, altering the total sample size is acceptable as long as 454 events could still eventually be observed. None of the other design features (total number of events, alpha-spending and power-accumulating functions) will be adaptively re-estimated or changed after the trial commences. To prevent bias, the decision to extend enrollment will be based only on overall (without regard to treatment group)

enrollment, withdrawal, and event rates. If this decision is required, it will essentially be a choice between enrolling additional patients to complete the study sooner or following 1800 patients longer.

All interim analyses (efficacy, futility, sample size re-estimation) will be performed by the unblinded statistician, who will serve as a liaison to the DSMB. The decision to terminate the trial due to efficacy or futility rests with the DSMB. It is the sponsor's decision whether to increase total enrollment.

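### The early-futility figures in Table 12.1-3 are not those of conditional power as Section 12.1.1.3.2 defines it: they match a final critical value of 1.96, whereas boundaries A and B lie at ±2.16

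*Combined protocol and SAP*

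**What the plan says.** The trial uses a Wang-Tsiatis "Design with K=18 Possible Analyses" (Section 12.1.1.2). Section 12.1.1.3 says "The vertical boundary is at analysis 18", running from −2.16 to +2.16, so a final statistic of, say, 2.05 falls on boundary C (no difference).

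Section 12.1.1.3.2 adds stochastic curtailment. Conditional power is "the chance of reaching boundary A or B under the alternative hypothesis, given the currently available data", and stopping is called futile when reaching boundary C is practically inevitable. The description of the simulation then calls conditional power "a function of observed log-rank test statistics, the information levels in Table 12.1-1, the overall significance level" and the true HR. It does not print the critical value.

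The threshold of 0.0001% is justified partly by two results: "there is a good chance (64%) of declaring futility early if the true HR is 1.0", and "there is little chance (2%) of declaring futility early if" the true HR is 0.75. The section states that "percentages can be assumed accurate to" ±0.2%. After Table 12.1-3, the plan starts the futility looks at Analysis 14 because "in none of the one million simulations was futility declared before Analysis 15".

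**The concern.** Section 12.1.1.3.2 points to two formulas. The definition by boundaries A and B, and the remark about boundary C, both imply 2.16 at the final analysis. The reference to the overall significance level suggests the two-sided 5% value, 1.96. The nominal level at Analysis 18 is 0.03058, not 0.05, because of the sequential design, so the two are not interchangeable.

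If the table came from the second formula, then its futility and boundary C columns, and the 64% and 2% used to support the threshold, do not describe the rule as defined. More practically, the unblinded statistician must program one formula, and some observed results would be futile under one and not under the other. Choosing between them after seeing unblinded data would be a data-dependent decision.

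**Working it through.** **Inputs.** Table 12.1-1: 18 looks at information fractions t = 0.15, 0.20, …, 1.00, with final variance V = 100.7. Table 12.1-2: final score boundary 21.70, so the final standardized boundary is 21.70/√100.7 = 2.162. With Δ = 0.1 the boundary at fraction t is 2.162 × t^(−0.4). Section 12.1.1.3.2: alternative HR 0.75 and threshold 10⁻⁶.

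**Model.** The score S at variance v is normal with mean −ln(HR) × v and variance v, with independent increments; positive S favors the S-ICD. I simulated one million paths per HR and checked against recursive numerical integration. HRs above 1 in Table 12.1-3 were taken as reciprocals (1.11 = 1/0.90).

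**The plan's own design figures reproduce.** Boundaries run from 4.62 to 2.16, rejection at HR 1.00 is 5.0%, and power is 80.0% at HR 0.75 and 93.6% at HR 0.70.

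**Conditional power.** With r = 100.7 − v remaining, b = c × √100.7 and θ = −ln(0.75) = 0.2877:

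CP = 1 − Φ[(b − S − θr)/√r] + Φ[(−b − S − θr)/√r]

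Here b = 21.70 for c = 2.162 and 19.67 for c = 1.96. Counting a crossing of A or B at any later look, rather than only the last, leaves the results for 2.162 unchanged for practical purposes (73.96% against 73.98% at HR 1.00).

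**Example.** Take an observed HR of 1.02 at Analysis 15 (v = 85.6). Then S = −ln(1.02) × 85.6 = −1.70, r = 15.1, √r = 3.89 and θr = 4.34.
- c = 2.162: (21.70 + 1.70 − 4.34)/3.89 = 4.90, so CP ≈ 4.7 × 10⁻⁷: futile.
- c = 1.96: (19.67 + 1.70 − 4.34)/3.89 = 4.38, so CP ≈ 5.9 × 10⁻⁶: not futile.

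**Chance (%) of futility before Analysis 18.**

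| True HR | Table 12.1-3 | c = 1.96 | c = 2.162 |
|---|---|---|---|
| 1.33 | 4.3 | 4.31 | 6.64 |
| 1.25 | 13.7 | 13.74 | 19.04 |
| 1.11 | 48.8 | 48.94 | 58.48 |
| 1.00 | 64.2 | 64.12 | 73.83 (73.9 by integration) |
| 0.90 | 38.2 | 38.05 | 46.86 (47.0 by integration) |
| 0.80 | 7.9 | 7.86 | 11.40 |
| 0.75 | 2.1 | 2.06 | 3.33 |
| 0.70 | 0.3 | 0.33 | 0.61 |

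The other three rows also match at 1.96: HR 1.54, 0.09 against 0.09; HR 1.43, 0.86 against 0.8; HR 0.65, 0.03 against 0.03. At HR 1.00 the split over Analyses 15/16/17 is 9.0/27.3/27.9 in the table, 8.9/27.3/27.9 at 1.96 and 24.5/25.6/23.8 at 2.162. Boundary C at HR 1.00 is 30.9% in the table and about 21% at 2.162 (100 − 5.0 − 73.9 = 21.1).

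**Other explanations tried.**
- One-sided conditional power gives futility well before Analysis 15, and totals of 83.0% (2.162) or 77.2% (1.96) at HR 1.00.
- Zero drift makes HR and 1/HR symmetric, but the table is not (2.1 at 0.75, 4.3 at 1.33).
- Keeping 2.162 and lowering the threshold to 10⁻⁸ gives a total of 64.4% at HR 1.00, but split 0/30.4/34.1.
- Critical values of 1.92 and 2.00 give 62.0% and 66.4% at HR 1.00.

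**Futility zones in observed HR.**

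| Analysis | c = 2.162 | c = 1.96 |
|---|---|---|
| 15 | 1.013–1.092 | 1.038–1.066 |
| 16 | 0.960–1.111 | 0.982–1.086 |
| 17 | 0.905–1.139 | 0.924–1.115 |

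**Analysis 14.** At the planned 362.6 events the lowest attainable conditional power is 1.3 × 10⁻⁶ with 2.162 and 1.2 × 10⁻⁵ with 1.96, so neither formula can stop there. With 2.162 the margin is thin: at 365 events (variance 2/9 of events) the minimum is 9.5 × 10⁻⁷. Table 27.3-1 projects 364.58 events at that look.

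**The case against.** The best defense is that the table is not miscalculated. The description of the simulation names the overall significance level as an input, and the table agrees with that at 5%; the phrase about boundaries A and B would then be a loose gloss. The ±0.2 concerns Monte Carlo error, and the table meets it for the rule apparently simulated. The search over alternatives was finite, and the reference cited for the formula is not available here.

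The consequences are also small. Any result in the disputed bands already has less than a one-in-a-million chance of reaching A or B under HR 0.75. The 1.96 rule only continues such trials a little longer: at HR 1.00, 423 expected events against 414, or about one month (67.4 against 66.4 at the 25% event rate). A good chance at HR 1.0 and a little chance at HR 0.75 remain fair descriptions of 74% and 3.3%. Futility is not automatic; the DSMB decides. Its charter or a separate SAP might fix the formula.

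Most of this stands and limits the weight of the point. It does not remove the conflict. The definition and the boundary C remark fix 2.16, the table behaves as 1.96, and the protocol prints neither value in the formula.

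**Conclusion.** The point holds. Under conditional power as defined, the chance of early futility is 73.9% at HR 1.00 and 3.3% at HR 0.75, not 64.2% and 2.1%; the gap is 3.5 to 9.7 points for HRs from 0.80 to 1.25. The table reproduces with 1.96, and with none of the other variants tried. That 1.96 was used remains an inference from this match and from the wording about the overall significance level.

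Type I error, power, efficacy boundaries, event target and the choice of threshold are unaffected. No stop before Analysis 15 is possible under either formula at exactly the planned information, though with 2.16 that statement is sensitive to a few extra events. The results assume the planned information fractions and the usual normal approximation for the log-rank score. This should be fixed, but it does not threaten the design.

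**What to change.** Print the critical value in the conditional power formula before any futility look, and carry the same formula into the SAP and the DSMB charter. Either route resolves the conflict:

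- **Use 2.16 (the Table 12.1-1 boundaries), to match the definition.** Rerun Table 12.1-3 and replace 64% and 2% with about 74% and 3.3%. The 0.0001% threshold and the Analysis 14 start can stay. Qualify the statement that no stop occurs before Analysis 15 as applying at the planned information.
- **Keep 1.96, if that was intended.** Print it and reword the definition so that it no longer speaks of reaching A or B. The table and percentages then stand.

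The first route costs one simulation run, one table, two percentages and a sentence; the second costs a sentence or two. Neither changes alpha, power, boundaries, event target or threshold.
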